8.2. Secondary analyses

As indicated above, the same basic model specified above can be used for the secondary outcomes, most of which are continuous. For a binary secondary outcome, we will use the logistic regression analog in which $g()$ above is the logistic function, $g(u)=\log\{u/(1-u)\}$. Since the strict interpretation of odds ratios from mixed models with the logistic link is dependent on the value of the random effect variable (participant), we will also use maximum likelihood estimation and robust variance estimation described for the primary analysis above. The same assumptions and methods for missing data for the primary outcome will also be used in the secondary analyses.

In particular, we seek to estimate the treatment effect for each of 5 lobes of the lung. A simple approach is to use the basic change-from-baseline model described above separately for data from each lobe and then use a gate-keeper Chi-square test and Bonferroni correction to account for the multiplicity of tests. This method, while valid, does not provide evidence about the correlation among the estimates from the 5 lobes that is itself of scientific interest. Therefore, we will use a multivariate version of the GLMM from Section 8.1 that simultaneously estimates the treatment effect for the 5 lobes and produces both the 5 estimates of treatment effect as well as their covariance matrix³⁸. We will use these results to conduct gate-keeper Chi-square test of the null hypothesis that the 5 treatment effects are all the same across lobes and if this null is rejected, provide lobe-specific treatment effect estimates with 99% Bonferroni-corrected confidence limits to ensure that the joint coverage probability is 95%. In addition, we will also show estimates and 95% confidence limits for the between lobes correlations.

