5.2. Secondary outcome measures

- Spirometry. FEV₁ and FVC are measured before and after 2 inhalations of albuterol in accordance with ATS/ERS standards and using NHANES reference values^{27 28}.
- Other HRCT measures. Emphysema (pct950) will be measured in each of the lobes of the lung separately. Other measures include TLC²⁹, mean lung density, 15th percentile density, and airway lumen and wall thickness will be measured for small, medium, and large airways³⁰.
- Respiratory questionnaires. The St. George's Respiratory Questionnaire for COPD Patients (SGRQ-C) is a widely used measure of disease impact as an indicator of disease-specific quality of life. The mMRC dyspnea scale (mMRC) will serve as our primary measure of dyspnea and be used for risk stratification³¹ The COPD Assessment Test (CAT) is designed to quantify the impact of COPD symptoms on the health status of participants³².
- Patient reported outcomes. The Patient Reported Outcomes Measurement Information System Questionnaire: Physical Function – Short Form 20a (PROMIS-20a) is used to indicate patients' state of wellbeing or suffering as well as their ability or lack of ability to function³³.
- Laboratory testing. Complete Blood Count (CBC) and Comprehensive Metabolic Panel (CMP) of blood chemistries will be obtained at local labs to detect hematologic, electrolyte, renal, or hepatic abnormalities that indicate exclusion from treatment or adverse events. Pregnancy tests will be done on women of child-bearing potential at each visit and prior to performing a HRCT scan
- Adverse effects to assess safety and tolerability are assessed by open-ended questions at each visit and rated in severity. Targeted symptoms, e.g. orthostasis, cough, and angioedema will be asked directly.
- Interval health history is recorded at each clinic visit. With participant permission, records of hospitalizations and deaths are obtained for verification of diagnoses and assessment of safety.
- Adherence is recorded at each visit by self-report and by capsule counts from returned containers.

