8.1. Primary analysis

The primary goal of analysis is to precisely estimate the difference in response between the losartan and placebo groups by comparing between-group means of changes from baseline pct950 over the time course of treatment. The secondary goals require estimation of analogous differences in response trajectories separately for each secondary response variable. For analytic methods, we propose a series of generalized linear mixed models (GLMMs) for responses (Y) with possibly g -transformed) expected primary or secondary responses, $g(E(Y_{ij}|b_{0i}, \beta_i X_{ij}))$, where 1.) $(\beta_0 + b_{0i})$ for the i^{th} patient response is a random intercept (to account for serial correlations in the within-patient responses) with fixed mean β_0 and random normal distributed offsets b_{0i} , with mean zero and standard deviation $\sigma_{b_{0i}}$ and 2.) X_{ij} are fixed values of j^{th} covariate for the i^{th} patient and β_i is the fixed unknown regression coefficient to be estimated for covariate X_j . Covariates will include site (14 binary spline indicator variables for the 15 category site stratification), baseline values of the Y response, an indicator variable for treatment group ($trt = 1$ losartan, 0 placebo), and either spline indicators for time or a continuous function for the fixed time trend in mean response, and, if needed, interaction terms between the time covariates and the (trt) treatment group indicator. The primary outcome is change in pct950 from baseline after 48 weeks of treatment ($Y = \text{pct950} - \text{pct950}_{b_i}$) and $g(\cdot)$ is the identity function, so the above model simplifies to $Y_i + \varepsilon_i = E(Y_i | b_{0i}, X_i) = \beta_0 + b_{0i} + \beta_1 trt + \beta_2 \text{pct950}_{b_i} + \{\beta_j X_{ij}\} + \varepsilon_{ij}$, where β_0 is the intercept for the fixed effects, b_{0i} is the normal $(0, \sigma_{b_{0i}})$ random intercept offset for each participant, β_1 is the primary losartan vs placebo treatment effect = mean difference in 48 week change in pct950 from baseline, losartan vs. placebo, $\{\beta_j\}$ is the set of regression coefficients to account for stratification by site, and ε_i is a normal $(0, \sigma^2)$ random error for the i^{th} change from baseline in pct950. The primary analysis will focus on β_1 , = mean losartan vs. placebo mean change over 48 weeks in pct950. We will estimate a 95% confidence interval for the losartan vs placebo mean difference, β_1 , using the regression estimate and the t -distribution; we will reject the null that losartan is equivalent to placebo if the 95% interval excludes 0.0. A robust variance estimate³⁷ will be used to guard against incorrect inferences due to misspecification of the assumed serial correlation structure among repeated observations on each subject.

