
The primary analysis will be intention-to-treat so that the indicator trt is the group to which the person is randomized without regard to whether they complied with the treatment assignment or not. We anticipate some degree of loss-to-follow-up (less than 10%) that will not affect our analyses. However, the regression model above will be estimated using the method of maximum likelihood so that missing data will effectively be imputed by their expected values given the other measurements. If the loss-to-follow is 10% or greater, then multiple imputation will be used to construct the 95% confidence limits for β_1 estimated across 50 imputations of the dataset.

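### Maximum likelihood with a robust variance leaves the mixed-model odds ratio participant-specific, so Section 8.2 does not resolve the interpretation problem it raises for repeated binary secondary outcomes

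*Combined protocol and SAP*

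**What the plan says.** Section 8.1 sets the primary goal as a comparison of group means and the secondary goals as the analogous between-group differences. The only model it describes has a random intercept for each participant. Section 8.2 carries this model to binary data: "For a binary secondary outcome, we will use the logistic regression analog". It then raises a difficulty, "Since the strict interpretation of odds ratios from mixed models with the logistic link is dependent on the value of the random effect variable", and gives its answer in the same sentence: "we will also use maximum likelihood estimation and robust variance estimation described for the primary analysis above".

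Section 8.1 also states what the two tools are for. The robust variance is there "to guard against incorrect inferences due to misspecification of the assumed serial correlation structure among repeated observations on each subject". The model is "estimated using the method of maximum likelihood so that missing data will effectively be imputed by their expected values", which is a missing-data purpose.

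No binary secondary outcome is named, and Section 8.2 says that most secondary outcomes are continuous. Section 5.2 does place adverse effects, assessed at each visit, among the secondary measures, and adds: "Targeted symptoms, e.g. orthostasis, cough, and angioedema will be asked directly". Separately, the safety review in Section 9.3 describes cumulative event percentages by severity, compared by treatment group. It mentions no odds ratio.

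**The concern.** With the identity link used for the primary outcome, the coefficient given the participant and the coefficient averaged over participants are the same number. With the logit link they differ once participants vary. Carrying the model over therefore changes the question from the effect of assignment on the arm proportions to the effect for a participant with a given random intercept. The authors evidently noticed this, but the tools they cite serve other purposes.

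What is at stake is interpretation. A reader of the trial report will take an odds ratio for losartan against placebo as a comparison of the two arms. If it is participant-specific and unlabelled, it will not match the arm proportions printed beside it and will suggest a larger contrast than they show. This matters only for a yes/no outcome recorded repeatedly and modelled under Section 8.2, such as symptoms asked about at each visit, if they are analysed that way.

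**Working it through.** **Plan's own figure.** The plan gives no odds ratio, event rate or random-intercept SD, so nothing on this point can be reproduced. Its one sample-size calculation (88 per group, 110 after inflation) concerns the continuous primary outcome. It is reproduced closely (86 per group by the t-based formula, power 0.91 at 88, and 88/0.8 = 110) and does not bear on this point.

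**Step 1: what each tool does.** In the model logit P(Y = 1 | b) = a + β·trt + b, with b ~ N(0, σ²):
- Maximum likelihood estimates a, β and σ jointly. exp(β) is the odds ratio at a fixed b.
- A robust (sandwich) variance replaces the estimated covariance of those estimates. The estimate of β is unchanged.

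Neither step averages over b. Section 8.2 describes no marginal model, no standardisation and no risk difference.

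**Step 2: size of the gap.** Assumed inputs, none from the documents: conditional odds ratio 2.0, so β = ln 2 = 0.693; control proportion 5%, 10%, 20% or 50%; σ from 0 to 3. The arm proportion is p(trt) = E[expit(a + β·trt + σz)] with z standard normal, evaluated by 80-point Gauss–Hermite integration. The intercept a is solved so that p(0) equals the control proportion. The marginal odds ratio is [p(1)/(1 − p(1))] / [p(0)/(1 − p(0))].

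| Random-intercept SD | 5% | 10% | 20% | 50% |
|---|---|---|---|---|
| 0 | 2.00 | 2.00 | 2.00 | 2.00 |
| 0.5 | 1.98 | 1.96 | 1.94 | 1.93 |
| 1 | 1.90 | 1.86 | 1.81 | 1.78 |
| 2 | 1.69 | 1.62 | 1.56 | 1.52 |
| 3 | 1.51 | 1.45 | 1.41 | 1.38 |

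Example at SD 2 and 10% on control: a = −3.417 and p(1) = 15.2%. The marginal odds ratio is (0.152/0.848)/(0.10/0.90) ≈ 1.62. A reader who took 2.0 as the between-arm value would infer odds of 2 × 0.111 = 0.222, which is 18.2% on losartan. With a conditional odds ratio of 1.0, the marginal odds ratio is 1.0 at every SD.

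SD 3 is an extreme case: the latent intraclass correlation is 9/(9 + π²/3) = 0.73. At SD 0.5 it is 0.25/(0.25 + 3.29) = 0.07.

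**Step 3: check by simulation.** Assumed settings: 150 trials, 110 per arm, 5 visits, a = −2, σ = 2, conditional odds ratio 2 (true marginal odds ratio 1.55).

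| Analysis | Mean log OR | OR | Mean SE | Rejection rate |
|---|---|---|---|---|
| ML, model-based SE | 0.620 | 1.86 | 0.340 | 0.41 |
| ML, robust SE | 0.620 | 1.86 | 0.340 | 0.41 |
| GEE | 0.389 | 1.48 | 0.216 | 0.40 |

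The robust step leaves the estimate alone. Both averages fall somewhat below their true values (0.693 and ln 1.55 = 0.44). The Monte Carlo error is about 0.02 to 0.03, and the two analyses share the same simulated data. Their ratio, 0.389/0.620 = 0.63, agrees with the true ratio 0.44/0.693 = 0.63. The conditional estimate is larger and so is its standard error, which is why the rejection rates hardly differ.

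**The case against.** **The sentence may intend a second, marginal analysis.** The word for an additional step appears in it. An ordinary logistic fit without the random intercept, with a variance robust to repeated observations, would be population-averaged, and this would explain why the sentence opens with the interpretation problem. The reading is possible, but it is not written. The sentence points back to Section 8.1, where the only model has the random intercept. If a marginal model was meant, the same sentence still needs rewriting.

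**A reader might infer that binary secondary and safety results would be overstated.** The documents do not support that:
- A conditional odds ratio is a different estimand, not a biased one. It exceeds the marginal one only when there is both an effect and between-participant variance.
- The one adverse-event analysis described, in Section 9.3, uses arm-level percentages, which are already marginal.
- Adverse effects are rated in severity, and no listed outcome is called binary. The point reaches symptoms only if they are modelled as repeated yes/no responses under Section 8.2.
- Death, or any outcome scored once per participant, gives one value each. The participant variance is then not separately identifiable, and the model in effect reduces to ordinary logistic regression.

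All of these limits stand. They narrow the point without making the stated remedy work.

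**GEE alone would not give the plain between-arm odds ratio.** This also stands. Section 8.1 says "Covariates will include site (14 binary spline indicator variables for the 15 category site stratification") together with the baseline response, so a GEE with those terms remains conditional on them.

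**Conclusion.** The point holds in a limited form. As written, Section 8.2 offers a remedy that does not act on the problem it names, and the odds ratio stays participant-specific. For a conditional odds ratio of 2.0, the marginal value would be about 1.9 to 2.0 at SD 0.5, 1.8 to 1.9 at SD 1, and 1.5 to 1.7 at SD 2. These figures rest on assumed SDs and on control proportions of 5% to 50%; the documents supply neither, so the true gap could be negligible.

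The gap is zero under the null, and conclusions about whether there is an effect should barely change. The identity-link primary analysis, the continuous secondary outcomes, outcomes recorded once per participant and the Section 9.3 percentages are unaffected. A claim that safety findings will be exaggerated goes beyond the text. This is an inexpensive correction to a secondary analysis, not a threat to the trial's main conclusion.

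**What to change.** Replace the sentence in Section 8.2 along these lines: *For repeated binary secondary outcomes, predictions from the fitted mixed model will be averaged over the random-effect distribution and the observed covariates to give a proportion for each arm. The marginal risk difference and marginal odds ratio will be reported with 95% confidence limits. Any odds ratio taken directly from the mixed model will be labelled participant-specific.* It would also help to name which secondary outcomes, if any, will be analysed this way.

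Standardisation serves the plan's between-group goal, deals with the site and baseline covariates as well as the random effect, and keeps the likelihood-based handling of missing data. GEE with a robust variance is an alternative, but it stays conditional on those covariates and needs a stronger missing-data assumption (missing completely at random) or weighting.

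The cost is one revised sentence and a little extra analysis work. No change to data collection, sample size or the primary analysis is needed.

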7.1. HRCT scans

HRCT scans of the lung will be acquired from individuals with COPD at V1 to confirm emphysema, and if eligible and randomized, at V7 (total of two scans). These data will be obtained specifically for research purposes using standardized protocols for different model scanners. Variation between scanners is minimized by designating the same scanner to be used for all scans on an individual before and after study treatment. The participant should have taken 2 puffs of albuterol within 6 hours of the HRCT scan.

For the HRCT scans:

- A pregnancy test will be administered at each visit before imaging for women of child bearing potential
- The lungs and trachea will be included
- The scanning protocol will begin below the lung bases and end above the lung apexes at the mandible
- Scans will be performed with the subjects in the supine position
- Each participant will have one standard scout (AP/PA) scan over the chest at Total Lung Capacity (TLC). Then a complete chest HRCT will be done at Total Lung Capacity (TLC)

Since the scans will be done at TLC, it is important for the coordinators and radiology technologists to ensure that the participant is appropriately coached prior to performing the actual scanning procedures. Study coordinators will be provided with a script to coach participants in the appropriate breathing technique to take and hold a TLC breath during spirometry prior to the HRCT exam. They will also provide the script for the radiology technologist to coach participants in the breathing technique. The scan will take about one hour including preparation and coaching. In order to minimize errors in scan acquisition, we will ask coordinators to accompany the participants to the HRCT scanner and provide the radiology technologist with the LEEP HRCT protocol including the proper acquisition parameters to program into the HRCT scanner. The model and serial identification number of the scanner will be recorded so that the same scanner is used for the second scan.

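### Section 8.2 appears to release the five lobar effect estimates only after a test that cannot detect an effect shared by all lobes

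*Combined protocol and SAP*

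**What the plan says.** Section 5.2 makes lobar emphysema a secondary outcome: "Emphysema (pct950) will be measured in each of the lobes of the lung separately". Section 8.2 gives the aim: "we seek to estimate the treatment effect for each of 5 lobes of the lung". It chooses a multivariate mixed model that "simultaneously estimates the treatment effect for the 5 lobes and produces both the 5 estimates of treatment effect as well as their covariance matrix".

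The reporting rule comes next. The plan specifies a "gate-keeper Chi-square test of the null hypothesis that the 5 treatment effects are all the same across lobes and if this null is rejected", it will "provide lobe-specific treatment effect estimates with 99% Bonferroni-corrected confidence limits to ensure that the joint coverage probability is 95" percent. The sentence after that carries no condition: "In addition, we will also show estimates and 95% confidence limits for the between lobes correlations".

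No significance level is attached to the gate. The 0.05 in section 8.5 and the 95% intervals in sections 8.1 and 8.4 belong to other tests. Nothing says what is shown for the lobes if equality is not rejected.

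**The concern.** The gate and the aim answer different questions. The aim is to learn the effect in each lobe; the gate asks whether the lobes differ. If losartan slowed emphysema equally in all five lobes, the gate would have no reason to open, however large the benefit, and a planned secondary result would go unreported. Failure to reject would not show that the lobes are alike either.

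There is a second, smaller issue. The 99% limits are said to ensure 95% joint coverage. That holds if they are always reported. It need not hold for the subset of trials in which the gate happened to open, and those are the only limits a reader would see.

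**Working it through.** **The plan's own figure.** Bonferroni over five lobes gives 1 − 0.05/5 = 0.99 per lobe, as stated. If the lobes were independent, joint coverage would be 0.99^5 = 0.951. The 99% level is right for ungated reporting.

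**Blindness to a shared effect.** The equality test depends only on differences between lobes. Adding one constant to all five effects changes no difference, so the noncentrality of the 4-df chi-square is zero for any common effect. The gate then opens with probability equal to its alpha. This needs no assumed SD or correlation.

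**Inputs for unequal effects.** From section 8.5: delta 2, SD 4 (whole lung), 88 or 110 per arm. Assumed, because the plan is silent: gate alpha 0.05, and an exchangeable between-lobe correlation ρ from 0 to 0.9. All lobes are read from the same scan (section 7.1), so positive ρ is plausible and ρ = 0 is the least credible value. Two bases for the lobar SD are used:

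- Basis A: SD 4 in each lobe.
- Basis B: whole-lung SD 4 with five equally weighted lobes, so lobar SD = 4/√((1+4ρ)/5), which is 8.9, 6.0, 5.2, 4.6 and 4.2 at ρ = 0, 0.3, 0.5, 0.7 and 0.9.

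**Formulas.** SE² = 2·SD²/n. The gate opens if Σ(estimate − mean)² / [SE²(1−ρ)] > 9.488, the 95th percentile of chi-square on 4 df. Noncentrality = Σ(effect − mean effect)² / [SE²(1−ρ)].

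Worked case: effects 1.6, 1.8, 2.0, 2.2 and 2.4 (±20%), basis A, 88 per arm, ρ = 0.5. The sum of squares is 0.16 + 0.04 + 0 + 0.04 + 0.16 = 0.40; SE² = 2·16/88 = 0.364; noncentrality = 0.40/(0.364·0.5) = 2.2; the gate opens in 18.6% of trials.

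**Percentage of trials in which the gate opens**

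| Effects | n per arm | Basis | ρ=0 | 0.3 | 0.5 | 0.7 | 0.9 |
|---|---|---|---|---|---|---|---|
| Equal, any size | either | A or B | 5 | 5 | 5 | 5 | 5 |
| 1.6 to 2.4 | 88 | A | 11.2 | 14.2 | 18.6 | 29.5 | 76.2 |
| 1.6 to 2.4 | 88 | B | 6.1 | 8.7 | 12.6 | 22.8 | 72.2 |
| 1.6 to 2.4 | 110 | A | 12.9 | 16.9 | 22.6 | 36.5 | 85.9 |
| 1.6 to 2.4 | 110 | B | 6.4 | 9.7 | 14.7 | 28.1 | 82.6 |

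For the ±20% pattern the gate reaches 50% only at ρ of about 0.83 (A) or 0.85 (B) with 88 per arm, and 0.79 or 0.82 with 110. With effects from 1 to 3 (±50%) and 88 per arm it opens in 53–100% (A) or 13–100% (B).

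**Joint coverage of the five 99% intervals, given an open gate, 88 per arm (simulation, %)**

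| Effects | Basis | ρ=0 | 0.3 | 0.5 | 0.7 | 0.9 |
|---|---|---|---|---|---|---|
| Equal | A or B | 52 | 70 | 79 | 88 | 95 |
| 1.6 to 2.4 | A | 75 | 85 | 90 | 95 | 98 |
| 1.6 to 2.4 | B | 59 | 79 | 88 | 94 | 98 |
| 1 to 3 | A | 93 | 95 | 96 | 97 | 98 |
| 1 to 3 | B | 78 | 92 | 95 | 97 | 98 |

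Without the gate, joint coverage is 95–98% throughout. The chance, over all trials, of reporting a set with at least one miss is at most 3.9% in any scenario run, so the gated procedure does keep that rate below 5%.

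**The case against.** The strongest reply is that the plan never says the estimates are withheld. It says what happens on rejection and is silent otherwise, the model yields the five estimates in any case, and section 8.1 states "The secondary goals require estimation of analogous differences in response trajectories separately for each secondary response variable". The condition might govern only the Bonferroni-limited display. This stands as a possible reading. But section 8.2 makes the effects conditional and the correlations, one sentence later, unconditional, so withholding is the more natural reading. The text does not settle it.

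A second reply is that showing lobe-specific effects only after evidence of heterogeneity is a recognised strategy, and that if the lobes are alike the ungated whole-lung estimate carries the message. That would suit a claim that lobes differ. It does not fit an aim of estimating each lobe, and with a true ±20% spread the gate usually stays closed unless ρ is very high.

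Third, the magnitudes rest on inputs absent from the plan, and the worst coverage figures occur at ρ = 0. Both points are fair. The coverage shortfall largely disappears with a ±50% spread at moderate ρ or above, and the chance of reporting a set with a miss stays under 5% overall. None of this touches the algebraic result for a shared effect.

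**Conclusion.** The concern holds. Followed as naturally read, the rule works against the plan's own lobar aim. For equal effects the conclusion is exact: the lobar estimates appear only at the gate's unstated error rate. For modestly unequal effects, whether they appear depends mainly on the between-lobe correlation, under the assumed alpha, lobar SD and exchangeable structure; at very high correlation or with large lobar differences the gate usually opens. The Bonferroni limits themselves are correct; what is not ensured is their joint coverage after selection by the gate.

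The harm is confined to this secondary analysis. The whole-lung primary estimate, the equality test and the between-lobe correlations are not gated, and primary power for delta 2 and SD 4 stays at 91% (88 per arm) or 96% (110 per arm). The plan should be changed, but the trial's main conclusion does not depend on it. Confidence is medium, because the withholding reading is natural rather than explicit.

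**What to change.** In section 8.2, remove the condition. State that all five lobe-specific effects from the multivariate model will always be reported with 99% limits, and that the equality chi-square will be reported separately as the heterogeneity result, with its significance level given. If always reporting was already the intent, one sentence saying so is enough.

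No new data or modelling is needed. The price is that five wide intervals are always shown. At 88 per arm the half-width is 2.576·SE, about 1.6 points if each lobe has SD 4. If the whole-lung SD is 4 (basis B), it is about 3.5, 2.3, 2.0, 1.8 and 1.6 points at ρ = 0, 0.3, 0.5, 0.7 and 0.9, or 3.1, 2.1, 1.8, 1.6 and 1.4 at 110 per arm. Against a delta of 2 points these intervals are imprecise, and the report should say so.
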